5.8 Follow-up Schedule

Participants will be scheduled for follow up appointments at 2 weeks, 6 weeks, 3 months, 6 months, and 1 year after the date of surgery. The 2 week visit is primarily a wound check to assess the wound and record any other surgical or medical complications that may have arisen since discharge. The remaining follow up appointments will include clinical evaluation, plain radiographs (AP and lateral views), and administration of the EQ-5D. The follow up schedule will be generated using the scheduling function in REDCap. All research clinic appointments will be conducted in a dedicated research clinic on Saturday afternoons. Every research clinic will be staffed by one of the study investigators ([name]), at least one research coordinator, and a research nurse.

Because the follow-up clinics occur on Saturdays, the following rounding system will be used to calculate which date the patient should come for a follow up visit:

- For patients that get operated on a Sunday, Monday, or Tuesday, the previous Saturday will be used to calculate the 2 week follow up date (and all other subsequent dates)
- For patients that get operated on a Wednesday, Thursday, Friday, or Saturday, the upcoming Saturday will be used to calculate the 2 week follow-up date (and all other subsequent dates)

Promoting Follow Up

The following strategies will be implemented in order to improve the rate of follow up:

1. Treating patients with a high level of hospital which involves:
 - a. Introducing the study participant to all members of the team
 - b. Advocating for timely and appropriate care of the patient
 - c. Clearly informing the patient about the steps of the study
 - d. Explaining the study to the contacts that the patient provided

- e. Protecting patient confidentiality
- 2. Calling the 3 contacts that the patient provides at the time of enrollment and notifying them of the patients illness, their participation in the study, and the importance of helping them attend all follow-up visits.
- 3. Costs of follow up care will be free to study participants, including the consultation fees and cost of plain x-rays.
- 4. Saturday clinic will be separate from the general clinic and conducted in private clinic offices. This will make it easier for patients to come back to MOI, minimize waiting times, and ensure patients are able to see a specialist rather than physician in training.
- 5. All patients will be contacted on the Wednesday prior to the Saturday clinic by phone as a reminder of the appointment time. A second reminder will be sent by text message on the day prior to the clinic.

No cash incentives will be provided to compensate for travel and other expenses. However, at the conclusion of 1 year, all patients who have been lost to follow up will be contacted by study staff to encourage return to the clinic. In cases where cost of travel is the principal barrier, a telephone follow-up evaluation will be conducted. The patient will also be asked to go to the nearest hospital, take follow-up x rays, and send in a picture of the x-rays. A picture of the patient performing the squat and smile test will also be requested.

5. 9 Study Financial Coverage

The following summarizes what is and what is not financially covered by the study. Any items not mentioned here need to be approved by the study review committee.

Covered	Not Covered

 - Ceftriaxone on admission - Ceftriaxone on subsequent surgeries that occur during the patient's first stay at the hospital - First dose of gentamycin * - First dose of metronidazole * - Consultation fees for follow-up clinics - Follow-up x ray images at 6k, 3mo, 6mo, 1yr - 2 week post-op control x-ray redo (if necessary) 	
 - Admission consultation and pre-op time - Cost of surgeries, implants ** - Post-op time in ward - Reoperations and all associated antibiotics and medications** - Exfix pin care methylated spirit - Knee brace - Physical therapy

* If the patient is not able to afford the remaining doses or has no relative who can purchase the antibiotics or will not be able to purchase the antibiotics in a timely fashion, these antibiotics will be provided for the patient at no extra cost

** While the study will not cover these items, the hospital may cover the cost if the patient is not able to afford

Study Steering Committee

The steering committee for the study will consist of [name], [name], [name], and [name]. The steering committee will be responsible for performing adjudication review, evaluating interim data, and approving any sub-projects.

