4.2 Sample Size

Data from two preliminary studies at MOI inform our projection for requisite statistical power. Our pilot study showed a difference in reoperation rate comparing external fixation and intramedullary nailing of 38% versus 3.8%, respectively. However, with longer follow-up and more stringent criteria for reoperation, we estimate a more conservative effect size is needed for power analysis. Therefore, to achieve 80% power (alpha=0.05) with a more conservative difference in the reoperation rate of 5% to 20%, the study would require 88 patients in each treatment group, or a total of 176 with completed follow up.

During the six month period from January to June 2012, MOI surgeons treated 238 patients presenting with open tibia shaft fractures, 50% (119) of whom suffered Gustilo Type 3A injuries - an incidence of approximately 20 patients per month. Our colleagues report the rate of open tibia fractures has continued to increase over the last two years and by current accounting, averages 25 patients with Gustilo Type 3A injuries per month. We therefore estimate an annual volume of approximately 300 qualifying injuries treated operatively at MOI. Assuming the majority meet inclusion criteria and a capture rate of 80%, we anticipate enrolling approximately 240 patients over a one year collection period. If the goal of 80% follow-up is met, a total of 192 patients will be included in our final analysis and we will achieve adequate statistical power. We will plan to conduct an interim analysis after six months to assess the accuracy of these initial estimates and determine whether the duration of the enrollment period should be altered.

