4.3 Timeline

November 2015:	Training, refinement, and implementation of study protocol
December 2015:	Begin study enrollment
January 2016:	1 month evaluation and consideration for protocol changes
June 2016:	Site visit for 6 month interim analysis and progress report
December 2016:	End study enrollment and 1 year site visit/interim analysis/progress report
June 2016:	Site visit for 18 month interim analysis and progress report
December 2017:	Complete follow-up data collection
March 2017:	Final data analysis

5. Study Procedures

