6.5 Follow-up Evaluation Form

This form is intended for use at all of the follow-up evaluations. These evaluations can be the Saturday in-person clinics or the ones done over the telephone in situations where the patient cannot come to clinic.

1. Follow-up visit number and type

- a. "Which follow-up evaluation?": Even though REDCAP automatically generates a new Follow-up Evaluation form at each evaluation time point, this form asks again what evaluation visit number this form is for. This is important because the questions for a 2 week visit are different from the 6 week to 1 year follow-up visit.
- b. It is important to properly answer the "Type of Follow-up Evaluation" question properly because what you say determines the types of questions that appear. Certain questions such as Range of Motion evaluation can only be answered in person.

Follow-up Visit	
Which follow-up evaluation? <small>* must provide value</small>	 2 Week  6 Week  3 Month  6 Month  1 Year <small>reset</small>
Record any reminders here to do for the patient during this follow-up visit: <small>Expand</small>	
Date of evaluation <small>* must provide value</small>	 <small>31</small>   Format is DD-MM-YYYY. Insert date manually, by clicking on the calendar image above, or press "Today" if applicable
Time from Surgery to Follow up	 
Type of Follow-up Evaluation **This is a key study question** <small>* must provide value</small>	 Patient attended Saturday clinic in-person  Telephone evaluation (missed clinic) <small>reset</small>
What is the reason for missing the appointment?	

2. Work

Return to Work		
Has the patient been working at all since the last follow-up visit?	 Yes  No	reset
Has their health status prevented them from going back to work?	 Yes  No	reset
Has their health status prevented them from working at their usual level?	 Yes  No	reset
Is this the first time the patient has gone back to work since the operation?	 Yes  No	reset

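### Sections 5.8 and 6.5 give different rules for telephone evaluation of patients who miss the one-year visit, and the December 2017 close leaves the last patients little tracing time

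*Protocol*

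**What the plan says.** **Who is evaluated by telephone.** Protocol section 5.8 (Promoting Follow Up) has study staff contact all patients lost to follow-up once one year is over, to encourage them back to the clinic. The telephone evaluation is then tied to one reason: "In cases where cost of travel is the principal barrier, a telephone follow-up evaluation will be conducted". Section 6.5, which governs the form for all follow-up evaluations, says they may be Saturday clinics or "the ones done over the telephone in situations where the patient cannot come to clinic". The form has a telephone option for a missed clinic and a field for why the appointment was missed.

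**When data collection ends.** Section 4.3 ends enrolment in December 2016 and sets "Complete follow-up data collection" for December 2017. The REDCap scheduling table before section 6.9 places the one-year visit at day 364, with 35 days allowed before and 120 after. Section 4.3 dates the final data analysis March 2017.

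**What depends on it.** The primary outcome in section 4.1 is reoperation within one year of definitive stabilization. Section 4.2 plans on follow-up as follows: "If the goal of 80% follow-up is met, a total of 192 patients will be included in our final analysis".

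**The concern.** The one-year contact carries much of the primary outcome. Section 5.8 schedules no visit between 6 months and 1 year, and the table in section 4.1 counts some events, bone grafting and nail dynamization among them, only beyond 6 months. For a patient who misses the last visit, no other scheduled contact would reveal those events.

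Patients stay away for reasons other than travel cost. The protocol foresees some of them: callers must reassure patients about unpaid bills and urge them to attend even when they feel well, and the complications form asks at which hospital a reoperation will be done. Staff who trace patients by section 5.8 alone would have no instruction to take an outcome by telephone from these patients.

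Absence may be related to outcome, for example in a patient reoperated on elsewhere. Missing data would then bias the comparison of arms, which a larger sample does not repair. Whether there was a reoperation, when, where and why can be asked without an examination, and section 6.5 hides only the examination items from telephone evaluations.

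**Working it through.** **1. The plan's own figures.** Section 4.2 aims "to achieve 80% power (alpha=0.05) with a more conservative difference in the reoperation rate of 5% to 20"% and states that "the study would require 88 patients in each treatment group, or a total of 176 with completed follow up". With two-sided alpha 0.05 (the sidedness is not stated, so this is an assumption) and a continuity-corrected comparison of two proportions, 5% against 20% gives 88 per arm. The stated figure is reproduced; without the correction it would be 76.

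- Expected analysed: 240 × 0.80 = 192. Expected lost: 240 − 192 = 48.
- Margin over the requirement: 192 − 176 = 16.
- Follow-up needed for 80% power: 176 / 240 = 73.3%.

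Continuity-corrected power is about 84% at 80% follow-up (192), 78% at 70% (168) and 70% at 60% (144). Power therefore tolerates a moderate shortfall. The greater risk is that missingness depends on outcome.

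**2. The two telephone rules.**

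| Patient who misses the one-year visit | Section 5.8 | Section 6.5 |
|---|---|---|
| Travel cost is the main obstacle | telephone evaluation | telephone evaluation |
| Cannot come for another reason | contacted, urged to return | telephone evaluation |
| Could come but does not | contacted, urged to return | not plainly covered |

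The second row is a contradiction and the third is a gap.

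**3. The calendar.** Inputs: target visit at surgery + 364 days; window opens 35 days earlier and closes 120 days later (364 + 120 = day 484). Data collection is taken to end on 31 December 2017, the latest reading of section 4.3.

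| Definitive surgery | Window opens | Day 364 | Window closes | Days from day 364 to 31 Dec 2017 | Days cut from window |
|---|---|---|---|---|---|
| 1 Dec 2016 | 26 Oct 2017 | 30 Nov 2017 | 30 Mar 2018 | 31 | 89 |
| 14 Dec 2016 | 8 Nov 2017 | 13 Dec 2017 | 12 Apr 2018 | 18 | 102 |
| 31 Dec 2016 | 25 Nov 2017 | 30 Dec 2017 | 29 Apr 2018 | 1 | 119 |

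Each row satisfies tracing days + days cut = 120. An earlier close in December shortens the tracing time further.

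**4. Who loses part of the window.** 31 December 2017 − 484 days = 3 September 2016, so only patients operated on by then keep all 120 days. With even accrual (an assumption) from 14 December 2015:

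- to 14 December 2016: 102 / 366 = 28%, and 0.279 × 240 ≈ 67 patients;
- to 31 December 2016: 119 / 383 = 31%, and 0.311 × 240 ≈ 75 patients.

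These patients have some shortening, from one day upward. They are not lost outcomes.

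**5. Final analysis.** March 2017 precedes the December 2017 end of data collection. If March 2018 was meant (an assumption), it would still precede the late-April 2018 end of the window.

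**The case against.** The strongest reply is that the protocol already does most of this. Section 6.5 and its form allow a telephone evaluation for patients who cannot come, and the reason field makes little sense if travel cost were the only permitted reason. Section 5.8 does not contain the word only, and it has all lost patients contacted. At least three telephone numbers are recorded and test-called, address details are kept for tracing, and reminder calls are repeated. This stands against the inference, which a reader of section 5.8 alone might draw, that telephone recovery is confined to patients who cannot pay for travel. It does not remove the difference between the two sections or the gap for patients who simply do not attend.

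A reader might also infer that data collection closes before the last patients' one-year window. It does not: for December 2016 surgery the window opens in October or November 2017 and day 364 falls by 30 December 2017. Only events within one year count, and the extra 120 days are a scheduling tolerance, not an outcome period. What is cut is time to find absent patients. That still matters, because section 5.8 starts tracing only when the year is over.

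It is also fair that a reoperation reported by telephone is not yet an adjudicated event. Section 5.10 has committee members vote on whether it is a primary outcome, so the call must collect enough detail for that vote. Finally, asking relatives about a patient's surgery raises confidentiality, which section 5.8 undertakes to protect.

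**Conclusion.** The concern holds as a conflict between sections 5.8 and 6.5, together with a close of data collection that leaves little time for tracing. Patients who stay away for reasons other than travel cost may have no one-year reoperation status recorded. For December 2016 surgery, at most about 1 to 31 days remain after day 364, and 89 to 119 days are removed from the end of the allowed window.

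The size of the loss is not known. A reader might take the 67 to 75 patients with a shortened window, or some share of the 48 expected losses, as outcomes lost or recoverable. The document supports neither: the first figure includes patients who lose a single day, and no recovery rate is given. The 80% follow-up goal may already count telephone evaluations.

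The dates assume a close on 31 December 2017 and last surgery between 1 and 31 December 2016. They are approximate, because enrolment ends when the sample size is reached (section 5.1) and its duration may be altered at the interim analysis (section 4.2). The change is still worth making: it is cheap and protects the primary endpoint from missingness related to outcome.

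**What to change.** - **Section 5.8:** replace the travel-cost condition with a telephone evaluation for every patient who misses the one-year visit for any reason, unless the patient declines contact. Record any reoperation with its date, hospital and indication, so that it can be adjudicated.
- **Section 6.5:** state the same rule.
- **Listed contacts:** use them to reach the patient. Ask them about outcomes only if the consent permits it.
- **Section 4.3, data collection:** set the end late enough after the last patient's one-year date to allow tracing. The latest point needed is last definitive surgery + 484 days, about April 2018 for enrolment ending in December 2016.
- **Section 4.3, final analysis:** give a date after that end, replacing March 2017.

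The cost is a few sentences, some more calls with the existing form, numbers and staff, and a final report up to about four months later. A shorter tracing period after the last one-year date would reduce that delay.

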5.10 Adjudication Review

Review of the following study events will require review from the members of the study steering committee:

1. Death of a patient
2. Delayed external fixation removal
3. Surgical complications requiring reoperation

The review, comment, and voting process will occur on REDCAP. 3 steering members will need to evaluate each event that is put up for review. The steering committee members are responsible for providing the following inputs for each event:

1. Comments/opinions/justifications
2. Vote (yes or no): question varies depending on the event
 - a. Death event: question not applicable
 - b. Delayed external fixation: does the patient need to remain on external fixator for an extended length of time?
 - c. Surgical complications requiring reoperation: does the patient need a reoperation?
3. Vote (yes or no): is this event a primary outcome of the study?

Adjudication review will be conducted every 2 months.

Final Reporting

At the conclusion of the study there will be a principal manuscript reporting the findings of the primary study endpoints.

On-Duty Schedule and Responsibilities

A research coordinator is required to be on duty at all times. A person will remain on-duty for three consecutive days. The transition to the next person on duty will occur at noon or in the early afternoon after the person on-duty has finished the morning tasks. During the transfer, the person on duty should notify the next person on duty about any pending items that need to be completed. These items should be written down in the on-duty diary.

Scheduling of the person on duty is to be done on an excel form available in the dropbox. Substitutions are permitted as necessary. The form is to be maintained and updated should any substitutions occur.

The following need to be provided for the on-duty coordinator:

- Study Laptop and USB Modem
- Study Phone
- Battery charge bank and wire
- On-call diary
- SIGN office key
- Antibiotics
- Wound measurement ruler
- On-duty diary

- Extra forms: consent, OTA wound classification, EQ-5D

Daily tasks for on-duty

To do in the morning:

- Patients in ward: (1) create follow-up schedule and (2) make sure they receive their antibiotics
- Patients in emergency: periodically check to see if there are any new patients
- Check in emergency logbook if there were any missed patients
- Patients waiting for operation: wait and randomize in OR
- Get the unused antibiotics from emergency room from last night
- Fill in on-duty diary

To do at night before leaving:

- Check for any new tibia patients
- Leave ceftriaxone (3 boxes and 3 waters for injection) for emergency
- Instruct emergency staff about the purpose of the antibiotics
- Remind emergency staff to contact the study phone for any open tibia patients
- Upload any images such as consent forms, radiographs, etc.

Tasks specific to the person on duty on Wednesday:

- Call patients scheduled to come for follow-up clinic on upcoming Saturday
 - If appointment confirmed with patient, go to calendar in REDCAP and change appointment status to “Scheduled”
 - If not scheduled, call repeatedly during the week until they are aware of the appointment
- Send text reminder to all patients on Friday*

* This duty falls on the person on duty on Wednesday because that person is most familiar with the patients who will come on that Saturday

Tasks specific to the person on duty on Saturday:

- Prepare records of patients for Saturday Clinic
- Contact the physicians that should be present at Saturday Clinic
- Manage Saturday Clinic
- Send review committee an email notification regarding the events that have occurred that need to be reviewed

To do whenever a new patient enrolls in the study:

1. Record details on REDCap
2. Ensure antibiotics are given promptly
3. Assess quality of pre-op x-ray and redo if necessary
4. Call 3 phone numbers and notify patient contacts of the study

When calling patients to remind them of their follow-up clinic, please notify them of the following:

- The clinic is entirely free
- It is important for them to attend the clinic to ensure their recovery is properly managed
- It is important for them to come to clinic even if they feel normal and healthy
- If they have not yet finished paying their hospital bill, we will not force them to pay their bill

After discharge, patient records go to the accounts department so that the patient can complete their bill. The records should be received from the accounts department after the bill has been paid. The records should then be stored in the SIGN Nail Office until the completion of the study.

6. REDCAP Procedures

General Principles

- All dates are to be recorded in the format dd-mm-yyyy.
- A new record is only created when data is saved into that record
- A new form is created only when data is saved into that form
- **This is a key study question

[figure not shown]
Adding a New Record

A record is the same as a study participant. The Participant ID will be automatically generated by the REDCAP system in ascending numerical order. REDCAP does not allow you to change or manually input the participant ID.

1. Click on “Add/Edit Records” on the left panel

2. Click “Add new record”

[figure not shown]

Editing an Existing Record

1. Click on “Add/Edit Records” on the left panel

2. Click on the drop down menu and select the desired record. Wait for the record to load.

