4.1 Outcomes

The primary outcome for our study will be composite, all-cause reoperation within one year of definitive skeletal stabilization, excluding bedside irrigation and debridement for superficial pin tract infections or planned ex-fix removal. The use of composite outcomes has been validated in a wide range of clinical trials.¹⁹ Primary events included in our composite outcome are detailed in the following table.

A participant who undergoes conversion from ex-fix to nail within six weeks of surgery will be analyzed according to the initial treatment that was assigned by randomization. Patients who undergo conversion from ex-fix to nail more than six weeks after the index procedure will be considered to have undergone a reoperation and will therefore count toward the primary outcome. Conversion from nail to ex-fix, regardless of time point, will be considered a primary outcome event.

Primary Events

Infection or hematoma	Repeat incision and debridement or drainage for superficial or deep infection or hematoma following initial wound healing.
Bone grafting	Bone grafting for patients > 6 months from index surgery. Bone grafting will be considered after 6 months in the case of delayed radiographic healing with > 2 months pain on attempted weight bearing.
Implant conversion (e.g. Ex Fix to IM nail) or implant exchange (e.g. exchange nailing)	Implant conversion or implant exchange > 6 months from index surgery to facilitate union.
Implant removal	
 1) For construct failure with appropriate clinical indication (broken hardware, half-pin failure at bone/pin interface). 2) Intramedullary nail removal to facilitate union. 3) Intramedullary nail removal due to patient reported pain or local irritation
Dynamization of intramedullary nail	
To facilitate healing > 6 months from index surgery.
 
* Note: Auto-dynamization without clinical indication for removal of broken component will not be counted as a primary event.

Osteotomy	To correct malalignment
Amputation	For limb salvage failure

Secondary clinical outcomes will include:

1. Post-operative compartment syndrome.
2. Superficial infection, as defined by CDC surveillance definitions, to include pin tract infections and cellulitis which resolves with use of antibiotics and local wound care.
3. Deep infection, as defined by CDC surveillance definitions, to include deep abscess or osteomyelitis.

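### Section 4.1 gives two incompatible rules for when an implant conversion is a primary event (after six weeks in the prose, after 6 months in the table)

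*Protocol*

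**What the plan says.** Protocol section 4.1 makes all-cause reoperation within one year the primary outcome, "excluding bedside irrigation and debridement for superficial pin tract infections or planned ex-fix removal". It then treats implant conversion in two places.

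- **Prose.** An ex-fix-to-nail conversion within six weeks is analysed under the randomized treatment. Beyond that, "Patients who undergo conversion from ex-fix to nail more than six weeks after the index procedure will be considered to have undergone a reoperation", and the sentence goes on to count this toward the primary outcome. For the other direction: "Conversion from nail to ex-fix, regardless of time point, will be considered a primary outcome event".
- **Primary Events table.** The prose introduces this table as giving the detail of the events in the composite. Its conversion row, which names ex-fix to nail as its example, reads "Implant conversion or implant exchange > 6 months from index surgery to facilitate union".

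Section 5.10 sends surgical complications requiring reoperation to the steering committee: "3 steering members will need to evaluate each event that is put up for review". One of the inputs is "Vote (yes or no): is this event a primary outcome of the study". That question does not mention section 4.1.

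**The concern.** Whether an operation belongs to the primary endpoint should follow from one written rule. Here a class of real reoperations has two written answers, and nothing in the protocol says whether prose or table governs.

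The class is foreseeable. Section 5.7 sets an ex-fix decision at 3 months, halfway between the two limits, and sends the option called other to adjudication. The follow-up form in section 6.5 gives conversion as an example of that option.

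Ex-fix-to-nail conversion can occur only in patients treated with ex-fix, so the choice of rule moves the event rate mainly in one arm. If the choice is made event by event, or after results are visible, the treatment comparison depends on a decision that was never fixed in advance. This is not a detail that a statistical analysis plan would normally supply, because the protocol itself fixes the endpoint and does so inconsistently.

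**Working it through.** **1. The two rules side by side (section 4.1)**

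| Operation | Prose | Table, conversion row |
|---|---|---|
| Ex-fix to nail, up to six weeks | analysed as randomized | not listed |
| Ex-fix to nail for union, six weeks to 6 months | event | not listed |
| Ex-fix to nail for union, after 6 months | event | event |
| Nail to ex-fix for union, before 6 months | event | not listed |
| Nail to ex-fix for union, after 6 months | event | event |

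The second and fourth lines conflict. The second is the clearer case, since no other table row covers an ex-fix-to-nail conversion done for union. In the fourth, the implant-removal row lists nail removal to facilitate union without a time limit and might catch the same operation. This is a further reason why the conflict bears mainly on the ex-fix arm.

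**2. The plan's own sample size**

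Inputs from section 4.2: 5% versus 20%, alpha 0.05 (taken as two-sided), power 80%. The mean rate is 0.125 and the difference 0.15.

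- Uncorrected: n = [1.960·√(2·0.125·0.875) + 0.842·√(0.05·0.95 + 0.20·0.80)]² / 0.15² = 75.1, so 76 per arm.
- With continuity correction: (75.1/4)·[1 + √(1 + 4/(75.1·0.15))]² = 87.9, so **88 per arm**.

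The stated 88 reproduces exactly.

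**3. What the choice of rule could do to power**

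The protocol gives no conversion rate, so I assume that conversions in the disputed window make up 2.5 or 5 percentage points of the ex-fix arm. With 88 patients that is 0.025·88 = 2.2 or 0.05·88 = 4.4 events. The nail rate is held at 5%. Power is the sum of Bin(x; 88, 0.05)·Bin(y; 88, p) over all pairs (x, y) for which the two-sided 0.05 test rejects, where p is the ex-fix rate. The protocol names no test, so three are shown.

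| Case | Ex-fix rate | Uncorrected chi-square | Fisher | Continuity-corrected chi-square |
|---|---|---|---|---|
| As planned | 20% | 88.3% | 83.8% | 82.2% |
| 20% includes them, not counted, 2.5 points | 17.5% | 77.7% | 70.9% | 68.1% |
| 20% includes them, not counted, 5 points | 15% | 62.1% | 53.4% | 49.7% |
| 20% excludes them, counted, 2.5 points | 22.5% | 94.5% | 91.9% | 91.2% |
| 20% excludes them, counted, 5 points | 25% | 97.7% | 96.4% | 96.1% |

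**4. What the pilot allows (section 2.3)**

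Of 26 ex-fix patients 2 were lost, leaving 24. Nine were reoperated (9/24 = 37.5%), 4 of them for delayed union (4/24 = 16.7%). Follow-up was 4.5 months, so all four fell before the table's limit. The pilot states neither the operation nor the week. If all four were ex-fix-to-nail conversions after six weeks, the prose gives 9/24 = 37.5% and the table (9 − 4)/24 = 20.8%. If none were, the two rules agree. These are bounds, not an estimate.

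**The case against.** **The table row covers only conversions done for union, so prose and table address different things.** This does not remove the conflict. The prose counts every ex-fix-to-nail conversion after six weeks whatever the reason, which includes those done for union.

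**All-cause reoperation governs, so the prose prevails.** This is a reasonable reading, but the protocol does not state it. It presents the table as the detail of the composite, and a time limit in that table has no purpose if every conversion counts anyway.

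**The conflict costs power.** A reader might infer this, but the documents do not support a direction. Section 4.2 says the planned rates allow for stricter reoperation criteria than the pilot's, and the pilot bound without delayed-union reoperations, 20.8%, lies close to the planned 20%. The 20% may therefore already leave early conversions out, in which case counting them adds power. This objection stands, and both directions are shown above.

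**The vote in section 5.10 itself biases the trial.** A reader might infer this because the inputs are asked for every reviewed event, including death and delayed ex-fix removal, and the exemption "Death event: question not applicable" is attached to a different question. The documents do not support it. Primary outcome is the term that section 4.1 defines, neither event is in that definition, and the natural vote on both is no. Nothing in the protocol suggests that such votes were or would be cast as yes. That the protocol does not say how three votes combine is missing detail and no error; three yes/no votes always yield a majority.

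**Conclusion.** The contradiction in section 4.1 is real and nothing elsewhere in the protocol resolves it. For an ex-fix-to-nail conversion for union between six weeks and 6 months, the prose and the table give opposite answers on the primary endpoint. A nail-to-ex-fix conversion before 6 months is affected too, though less clearly, because of the implant-removal row.

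The effect is mainly in the ex-fix arm. It may be zero if no such conversions occur. The power range of 62.1% to 97.7% around 88.3% (uncorrected chi-square) rests on assumed shares of 2.5 and 5 points, two-sided alpha, 88 per arm and a nail rate fixed at 5%. It shows sensitivity and predicts nothing. It should not be read as saying that the sample size is wrong.

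The point should be acted on: the endpoint rule is inconsistent as written and the correction is cheap. The adjudication vote matters only because it inherits the inconsistency.

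**What to change.** 1. Reconcile the prose and the Primary Events table in section 4.1 so that one written rule decides when a conversion in either direction counts as a primary event. Which time limit applies is for the sponsor and investigators to settle; this review does not choose one. The reconciled text should also make clear how the conversion row relates to the implant-removal row.
2. Apply that rule to every conversion in both arms. Re-check any conversion already adjudicated between six weeks and 6 months, and any earlier nail-to-ex-fix conversion. Ideally, settle the rule without reference to results by arm.
3. As a minor consequential edit, word the primary-outcome vote in section 5.10 as: *Does this event meet the section 4.1 definition?*

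The cost is wording edits in sections 4.1 and 5.10, the same edit wherever the vote is recorded, and a re-check of any affected events. No new data, staff or sample size change is needed.
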